6.1 Primary objective

The primary objective is to evaluate effects of CFZ533 on pancreatic beta cell function in subjects with new-onset T1DM.

6.1.1 Variables

Normalized stimulated C-peptide AUC, defined by stimulated C-peptide $AUC_{0-2\text{ hrs}}$ by mixed meal tolerance test (MMTT) after 52 weeks, divided by the actual duration of measurements, is the primary analysis variable. This variable is derived from the blood samples taken for C-peptide determination over the course of 2 hours: at baseline (average of $t = -10$ and $t = 0$ C-peptide values), and at 15, 30, 60, 90, and 120 min after completing consumption of the liquid meal. AUC will be calculated by linear trapezoid rule under the stimulated C-peptide concentration curve. At a minimum the baseline and 120 min (first and last) concentrations must be available to compute the AUC. Under linear trapezoid rule, if there are concentration missing for time points between first and last observed time point during the 2 hours window, this part of area under the curve will be covered by the trapezoid constructed by the closest neighboring time points with concentration values. Commercially Confidential Information

Actual time between each concentration measurement will be used during the calculation. If the total duration of measurement is >120 minutes, the trapezoid will be truncated at 120 minutes.

Baseline stimulated C-peptide AUC will be derived from the last set of C-peptide values collected before the start of study treatment.

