Urinalysis ⁷	X	X			X
Coagulation parameters					
Hematology	X	X	X		X
HbA1C		X			X
Clinical Chemistry	X	X			X

	Period	Follow-up Period				
		Visit Name	Wk 56 ³	Wk 60 ³	Wk 64 ³	Wk 68 ³
	Days		393 ±7	421 ±7	449 ±7	477 ±7
Pregnancy ⁸		S	S	S	S	
Thyroid function tests						
HLA						
Diabetes Autoantibodies		X			X	
Serology for vaccines ⁹						
Viral Load/serology for EBV, HSV, CMV ¹⁰					X	
Hepatitis and HIV screen						
Tuberculosis test						
Immunoglobulin CCI				X		X
Commercially Confidential Information						
PK blood collection ¹³		X	X	X	X	X

Commercially Confidential Information

Adverse Events	X	X	X	X	X
Study completion information					X

“S” denotes source data only.

¹ The screening and baseline evaluations continue until the first dose of study drug is administered. Investigators should note that the turnaround time for screening and baseline laboratory assessments range from 4 to 21 business days and visits should be planned to ensure reporting of inclusionary and safety labs. Turnaround times of laboratory measures are provided in the SOM under section 1.2. Study months equal 28 days or 4 weeks. Screening and Baseline evaluations may be done over one or more visits. World Health Organization and European Medicine Agency recommendations for trial related blood volume will not be exceeded. All inclusion/exclusion assessments must be resolved and reviewed prior to CFZ533 administration.

² First dose of CFZ533 is to be administered as early as possible following diagnosis of T1DM and within a 56 day interval from the time of diagnosis, however the interval from diagnosis to first study drug administration may be extended to 100 days in the event a screening assessment needs to be confirmed or vaccination is required.

³ This visit may be performed in clinic or scheduled as an off-site visit at an off-site location as allowed by local laws and regulations

⁴ Abbreviated Physical exam can be done after day 1 visit. Exam of the thyroid must be included in all physical exams.

⁵ Bone age assessments will be performed on all subjects aged 12-17 at screening. Assessments at subsequent visits will only be performed if bone age is < 17 years

⁶ Glucose and C-peptide will be done in serum, at the time of MMTT, 6 timepoints.

⁷ Including the assessment of creatinine, and C-peptide concentration in urine.

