8.2.1 Mixed Meal Tolerance Test (MMTT) for glucose and stimulated C-peptide

The mixed meal tolerance test (MMTT) has appropriate sensitivity to detect residual insulin secretion and beta cell function. In the MMTT, following an 8-10 hour overnight fast, a weight-based liquid meal provided as 6 mL/kg (maximum 360 mL) of mixed meal (Ensure Plus, Abbott, see Site Operations Manual), ingested over 5 min with timed blood samples for glucose and C-peptide determination obtained 10 min prior to ingestion ($t = -10$), at baseline ($t = 0$), and at 15, 30, 60, 90, and 120 min after consumption of the liquid meal ([Leighton et al 2017](#)). The time collections for post load samples are based on the start time of the mixed meal.

Blood sample collection will allow measurement of area under the curve (AUC_{0-2 hr}) and peak C-peptide values. MMTT will be collected at baseline, at Weeks 12, 24, 36 and 52 on treatment, and at Week 72 (End of study) visit. The primary efficacy endpoint is the treatment effect on stimulated C-peptide AUC_{0-2 hrs} by mixed meal tolerance test (MMTT) at Week 52 (12 months). Detailed instructions for subjects regarding fasting requirements are summarized in Site Operations Manual.

Proportion of subjects with detectable C-peptide, rate of decline from baseline C peptide; time to undetectable C peptide will be assessed. A timed urine for C-peptide:creatinine ratio will also be assessed as a measure of beta cell function.

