12.8 Sample size calculation

12.8.1 Primary endpoint(s)

The sample size calculation is based on the primary endpoint of stimulated C-peptide AUC by the standard MMTT.

In [Greenbaum \(2012\)](#) the average baseline stimulated C-peptide AUC by MMTT is approximately 0.7 pmol*hr/mL. They show a linear decline in untreated subjects resulting in an average AUC of 0.4 pmol*hr/mL at one year. It is assumed that a clinically significant prevention of decline would occur if the rate of decline was one half (50%) of that of untreated subjects. Thus, a clinically relative improvement due to treatment would occur if the AUC at 1-year was 37.5% larger for treatment than placebo ($0.55/0.4 = 1.375$). Starting with 44 subjects and accounting for ~18% dropout rate, a total of 36 subjects randomized in a 2:1 ratio (stratified by age at first screening visit: ≥ 18 to 21 years, ≥ 12 to < 18 years) between CFZ533 and placebo provides 55% power to detect an improvement over placebo using a one-sided alpha=0.1 test when the true ratio of treatment to placebo is 1.375 (Note: if the rate of decline in treatment vs placebo is instead 75% less, corresponding to a ratio of 1.56, the power is 75%). This calculation assumes a coefficient of variation of 70% for the AUC; the standard deviation of log (AUC) was derived from the relationship between the CV and variance parameter for the lognormal distribution. This assumption was the result of the observed CV% of 5 TrialNet studies in T1DM subjects ([Bundy et al 2016](#)).

13 Ethical considerations and administrative procedures

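### Should the primary C-peptide AUC require a minimum number of samples between fasting and 120 minutes?

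*SAP*

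**What the plan says.** SAP 6.1.1 defines the primary variable as the 0 to 2 hour C-peptide AUC divided by the actual duration of measurement. The fasting value is the mean of the -10 and 0 minute samples. Later samples are taken "at 15, 30, 60, 90, and 120 min after completing consumption of the liquid meal". The method is stated: "AUC will be calculated by linear trapezoid rule under the stimulated C-peptide concentration curve". The completeness condition is "At a minimum the baseline and 120 min (first and last) concentrations must be available to compute the AUC". If samples between the first and last are missing, "this part of area under the curve will be covered by the trapezoid constructed by the closest neighboring time points with concentration values". Actual sampling times are used, and the curve is cut at 120 minutes. A redacted block stands directly after the bridging rule.

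No visible limit on the number of missing intermediate samples appears in protocol 8.2.1, protocol 12.4, the per-protocol criteria in SAP 4.2, or the sensitivity analysis in SAP 6.1.3.3. SAP 1.1 places specifications for derived variables in a separate programming document that is not part of the public text.

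Two related wordings differ. Protocol 8.2.1 says "The time collections for post load samples are based on the start time of the mixed meal", whereas the SAP counts from completion of the meal. Footnote 6 of protocol Table 8-1 says "Glucose and C-peptide will be done in serum, at the time of MMTT, 6 timepoints", whereas protocol 8.2.1 lists seven draws.

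**The concern.** The bridging rule has no visible cap. With the 15, 30, 60 and 90 minute samples all missing, the nearest neighbours are the fasting and 120-minute values, and their plain mean enters the log-AUC model as if it were a full curve. That is a different quantity. The endpoint is meant to capture stimulated secretion, yet half of this value is the fasting concentration, and any peak before 120 minutes is lost.

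The sample size rests on about 12 evaluable placebo subjects, so a single low value there could flatter the drug. The same derivation also supplies the baseline covariate, every visit in the repeated-measures model, and the Week 72 endpoint. If sparse curves were excluded only after unblinding, the exclusion would look driven by the data.

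**Working it through.** **Inputs.** Evaluable subjects: 36, allocated 2:1, so 24 and 12. One-sided alpha 0.1, target ratio 1.375, and "This calculation assumes a coefficient of variation of 70% for the AUC" (all protocol 12.8.1). Sampling times and trapezoid rule from SAP 6.1.1. Curve shapes are assumed, because the documents give none.

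**The plan's own figure.** SD of log AUC = sqrt(ln(1 + 0.70²)) = 0.6315. SE of the log ratio = 0.6315 × sqrt(1/24 + 1/12) = 0.2233. Then ln(1.375)/0.2233 = 0.3185/0.2233 = 1.426, and power = Φ(1.426 - 1.282) = 55.8%. The noncentral t with 34 df gives 55.1%. The stated 55% is reproduced.

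**Weights.** Over 120 minutes the six curve points carry 7.5, 15, 22.5, 30, 30 and 15 minutes. The four intermediate samples hold 97.5/120 = 81.25%, fasting 6.25% and 120 minutes 12.5%. With two points the weights are 50% and 50%.

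**Effect per curve.** The table divides the AUC from the retained samples by the six-point AUC, for assumed concentrations in pmol/mL at 0, 15, 30, 60, 90 and 120 minutes. The shift in the log ratio from one two-point placebo curve is -ln(r)/12, where r is the two-point ratio. RMSE is sqrt(0.2233² + shift²).

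| Assumed curve | Two points (r) | Fasting, 60, 120 | Fasting, 15, 90, 120 | Shift | RMSE if kept |
|---|---|---|---|---|---|
| linear, .25 to .55 | 1.000 | 1.000 | 1.000 | 0 | 0.2233 |
| .25 .30 .38 .50 .53 .55 | 0.888 | 0.999 | 0.951 | 0.0099 | 0.2235 |
| .25 .31 .42 .56 .58 .52 | 0.797 | 0.978 | 0.933 | 0.0189 | 0.2241 |
| .28 .36 .48 .60 .58 .45 | 0.725 | 0.958 | 0.918 | 0.0268 | 0.2249 |
| .25 .38 .52 .62 .55 .42 | 0.663 | 0.944 | 0.892 | 0.0343 | 0.2259 |
| .25 .36 .46 .50 .40 .25 | 0.620 | 0.930 | 0.885 | 0.0398 | 0.2268 |
| .25 .45 .65 .75 .55 .25 | 0.455 | 0.909 | 0.830 | 0.0657 | 0.2327 |

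In the six non-linear shapes the treatment ratio rises by exp(shift) - 1, which is 1.0% to 6.8%. As a share of the SE, the shift runs from 0.0099/0.2233 = 4% to 0.0657/0.2233 = 29%. One active curve among 24 lowers the ratio by half as much on the log scale. Two of 24 active and one of 12 placebo cancel exactly when r is the same. A 10-point difference between arms in the share of two-point curves shifts the log ratio by 0.1 × -ln(0.797) = 0.023 or 0.1 × -ln(0.663) = 0.041.

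**Would a stricter rule help?** A natural remedy is to require two of the four intermediate samples, including 60 or 90 minutes, and otherwise to treat the visit as missing. It would reject fasting, 60 and 120 minutes (0.909 to 1.000) and accept fasting, 15, 90 and 120 minutes (0.830 to 1.000). The accepted pattern is the less accurate one in all six non-linear shapes.

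Dropping one placebo value at Week 52 gives SE = 0.6315 × sqrt(1/24 + 1/11) = 0.2299. Keeping a two-point curve gives a smaller RMSE in five of the six non-linear shapes (0.2235 to 0.2268), and a larger one only in the steepest (0.2327). The break-even is -ln(r) = 12 × SD × sqrt(1/11 - 1/12) = 1.0445 × SD. At SD 0.6315 this is r = exp(-0.660) = 0.52. If baseline adjustment halved the SD to 0.316 (an assumption), it would be r = exp(-0.330) = 0.72, and the three steepest shapes would favour dropping.

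**Side points.** Averaging the -10 and 0 minute samples turns seven draws into six curve points, which fits the footnote. For the meal clock, protocol 8.2.1 has the meal taken over 5 minutes. Smooth curves through five of the shapes gave an AUC ratio of 0.991 to 1.029 when sampling starts from completion rather than start of the meal. The ratio was 1.014 to 1.018 when samples drawn on the protocol clock are analysed on the SAP clock.

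**The case for a change.** The best case for a change is that this is the derivation of the primary variable, a sentence would settle it before unblinding, and the error is zero or downward in every curve assumed. On these shapes the stricter rule also reduces the worst error from 55% to 17%. The phrase about a minimum could be read as necessary but not sufficient, yet the uncapped bridging rule makes two points sufficient as printed.

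Most of the description stands: the visible text does permit a two-point AUC, and such an AUC can be well off for that one subject and visit. What does not stand is the step to a defect. The redacted block sits exactly where a limit would be written, and redacted text cannot be counted as absent. Nothing is left open after unblinding either, since method, minimum, bridging, clock times and truncation are all fixed.

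The pattern itself requires four consecutive samples to be lost while both ends are obtained. In protocol Table 8-1 the post-baseline meal-test visits are not marked as possible off-site visits, and protocol 8.2 allows an indwelling cannula. The reduction in worst-case error is real for the curves kept. It is bought by deleting visits, some of them more accurate than those retained. With strong borrowing across visits or a smaller residual SD the balance could tip the other way, so the comparison is close and favours neither rule clearly.

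**Conclusion.** No change to the plan. The printed rule for incomplete curves is simple, fixed in advance and the same for both arms. A stricter one would exchange a little bias for a little variance with no demonstrated gain. The likely effect is about 1% to 4% on the treatment ratio per two-point placebo curve, and 6.8% for the steepest shape. If such curves are balanced between arms, they mainly add noise. In a trial the protocol calls non-confirmatory, that is small beside a target ratio of 1.375.

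This rests on assumed curve shapes, on one or very few sparse curves, and on the protocol's 70% CV without credit for baseline adjustment. A marked difference between arms in missed samples would alter the picture, but nothing in the documents suggests one. Counting incomplete profiles by arm and visit, or rerunning the model without them, is ordinary reporting that analysts can add without touching the primary analysis. The meal-clock wording is a clerical mismatch worth about 3% or less and similar in both arms. The six-timepoint footnote agrees with the SAP once the two fasting draws are averaged.

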6.1.2 Descriptive analyses

Normalized stimulated C-peptide AUC (Weeks 12, 24, 36 and 52 on treatment and Week 72), its change and percent change from baseline will be listed by treatment, subject and visit. Summary statistics will be provided for raw value, change and percent from baseline by treatment and visit/time and will include mean (arithmetic), SD, CV (arithmetic), median, minimum and maximum. In addition, geometric mean/CV will be provided for raw value.

6.1.2.1 Graphical presentation of results

Geometric mean (80% CI) of normalized stimulated C-peptide AUC and ratio to baseline will be plotted by visit and treatment. Spaghetti plots of normalized stimulated C-peptide AUC and percent change from baseline of all individuals will be given by treatment.

6.1.3 Statistical model, assumptions and hypotheses

The primary statistical analysis will be done using the Full analysis set (treatment policy estimand). As a secondary analysis, the model will be run using the Per Protocol set (hypothetical strategy estimand). For both analyses, all data collected for subjects in the respective analysis sets will be used in the model (e.g. including data after study drug discontinuation). Stimulated C-peptide AUC by the standard MMTT, normalized by the duration of measurements, will be analyzed with a mixed model repeated measures (MMRM) analysis. The natural log of the AUC (Weeks 12, 24, 36 and 52 on treatment) will be the dependent variable in this analysis. Independent variables will include age group (≥ 12 to < 18 , ≥ 18 to 21) treatment, visit, and the treatment by visit interaction.

The natural log of the baseline AUC will be used as a covariate and subject will be used as a random effect. Back transformation (exponential) will be used to obtain the least square geometric mean of each treatment, the ratio of CFZ533 to placebo, the 80% confidence interval of the ratio, and the one-sided p-value of treatment benefit for each time point. The model-based estimated fixed effects and p-values will be presented, along with the overall treatment effect.

Note 1: Any C-peptide AUC collected at a post-baseline unscheduled visit will be assigned to the closest scheduled visit for the model-based analysis; in the case of a tie it will be assigned to the previous visit (e.g. unscheduled collected at Week 30 will be assigned to Visit 24 for the model-based analysis). If a C-peptide AUC is already available at the scheduled visit, the average of the scheduled and unscheduled visit AUC will be used in the model.

Note 2: Week 52 C-peptide AUC which was not actually collected 365 +15 days after the first dose (i.e. due to it being the EOT assessment for early treatment discontinuation) will not be used for the model-based analysis as a Week 52 assessment, but will be assigned to the closest visit.

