Subjects receiving CFZ533 therapy who will be travelling to an area of the world with endemic disease, *e.g.*, tuberculosis, dengue, Chagas disease, etc. for which they have not been vaccinated or no vaccine exists should be informed of a potential increased infection risks. Of note, subjects treated with CFZ533 can mount recall immune responses after the drug has been eliminated.

Subjects might be asked to complete an optional questionnaire to provide feedback on their clinical trial experience. Refer to the Site Operations Manual for a complete list of ICFs included in this study.

The study includes the option for the subject to have certain study procedures performed off-site by an OHP instead of at the study site, for which a signature on a separate consent form is required if the subject agrees. It is required as part of this protocol that the Investigator presents this option to the subject, when permitted by national and local governing regulations and deemed appropriate by the Investigator. The process for obtaining consent should be exactly the same as described above for the main informed consent.

8 Visit schedule and assessments

Assessment schedule lists all of the assessments and indicates with an “X” the visits when assessments are performed. All data obtained from these assessments must be supported in the subject’s source documentation.

Subjects should be seen for all visits/assessments as outlined in the assessment schedule or as close to the designated day/time as possible. Missed or rescheduled visits should not lead to automatic discontinuation. Subjects who prematurely discontinue study dosing should be encouraged to continue in study, off drug. Those who prematurely fully withdraw consent or discontinue the study for any reason should be scheduled for the end of treatment visit as soon as possible, at which time all of the assessments listed for the final visit will be performed. At this final visit, all dispensed investigational product should be reconciled, and the adverse event and concomitant medications recorded on the CRF.

Specification and timing of each assessment are detailed in the protocol.

Table 8-1 Assessment Schedule

Commercially Confidential Information

Commercially Confidential Information

Period	Screening ¹		Treatment															
Visit Name	Screening	Baseline	Day 1 ²	Wk 1	Wk 2 ³	Wk 4 ³	Wk 8 ³	Wk 12	Wk 16 ³	Wk 20 ³	Wk 24	Wk 28 ³	Wk 32 ³	Wk 36	Wk 40 ³	Wk 44 ³	Wk 48 ³	Wk 52 or EOT ²⁰

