12.4.3 Handling of missing values/censoring/discontinuations

Safety and efficacy data at key time points will not be imputed for the primary analysis. Data from subjects who discontinue study treatment will be excluded, from the date of study drug discontinuation from the primary efficacy analysis. The primary analysis based on mixed model repeated measurements for Stimulated C-peptide AUC measurements at various visits is valid under the assumption that the missing data are missing at random (MAR).

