4.2 Analysis sets

For subjects whose actual treatment received does not match the randomized treatment, the treatment actually received will be used for the analysis, except for analyses using the Full analysis set.

The Per-protocol analysis set includes subjects compliant with the protocol and is characterized by the following criteria:

1. Subject received at least 9 months of the randomized treatment,
 - a. Within those 9 months, subject received at least 75% of the planned doses.
2. Subject does not have any major protocol violations (See [Table 4-1](#))

The Full analysis set includes all subjects to whom study treatment has been assigned by randomization. According to the intent-to-treat principle, subjects will be analyzed according to the treatment they have been assigned to during the randomization procedure.

The safety analysis set will include all subjects that received any study drug.

The PK (Pharmacokinetics) analysis set will include all subjects with at least one available valid (i.e. not flagged for exclusion) PK concentration measurement, who received any study drug and experienced no protocol deviations with relevant impact on PK data.

The PD (Pharmacodynamic) analysis set will include all subjects who received any study drug with at least a baseline or one post-baseline PD assessment.

The analysis sets and protocol deviation codes are related as follows:

Table 4-1 Protocol deviation codes and analysis sets

Category Deviation code	Text description of deviation	Data exclusion
Subjects are excluded from PP analysis set in case of these PDs:		
Inc04	Deviation from inclusion criterion 4-Evidence of one or more T1D autoantibody(ies): anti-GAD, protein tyrosine, anti-IA-2, anti-ZnT8 and anti-ICA.	Exclude subject from PP analysis set
Inc06	Deviation from Inc06-Peak stimulated C-peptide \geq 0.2 nmol/L after standard liquid MMTT when subject is metabolically stable, at least 2 weeks from diagnosis and within 56 days prior to randomization.	
Exc01	Any other diabetes present except auto immune type 1, by judgement of the investigator.	
Exc18	Ongoing, and up to 2 weeks prior to screening, use of medications that may affect glucose control (e.g., systemic steroids, thiazides, beta blockers).	
Subjects are excluded from PP and PK analysis set in case of these PDs:		
Exc20	Taking medications prohibited by the protocol	Exclude subject from PP and PK analysis sets
Subjects are excluded from PP analysis set in case of these PDs:		

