OTH01	Subject potentially unblinded	Exclude subject from PP analysis sets
OTH02	Inv or Site Staff- Unblinded	Exclude only data after the date of unblinding
		Exclude only data after the date of unblinding

If updates to this table are needed, an amendment to the SAP needs to be implemented prior to DBL.

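### The per-protocol analysis is labelled a hypothetical-strategy estimand, but it selects on treatment received and keeps off-drug data, so it does not estimate the effect of continued treatment

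*SAP*

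**What the plan says.** SAP 6.1.3 makes the full analysis set (FAS) primary under a treatment-policy strategy, then adds: "As a secondary analysis, the model will be run using the Per Protocol set (hypothetical strategy estimand". Of both runs it says that "all data collected for subjects in the respective analysis sets will be used in the model (e.g. including data after study drug discontinuation".

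SAP 4.2 defines the PP set partly by behaviour after randomisation: "Subject received at least 9 months of the randomized treatment" and "Within those 9 months, subject received at least 75% of the planned doses". Subjects must also be free of the listed major deviations. The only partial data cut in Table 4-1 is for unblinding: "Exclude only data after the date of unblinding". There is none for drug discontinuation.

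Protocol 12.4.3 takes a different line for its primary analysis: "Data from subjects who discontinue study treatment will be excluded, from the date of study drug discontinuation from the primary efficacy analysis". It then relies on the mixed model under missing at random (MAR).

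Off-drug values should exist, because protocol section 8 says: "Subjects who prematurely discontinue study dosing should be encouraged to continue in study, off drug".

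**The concern.** A hypothetical strategy for discontinuation asks what Week 52 C-peptide would have been, in everyone randomised, had nobody stopped. The PP run departs from that in two ways.

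- **Selection.** It conditions on remaining treated for 9 months. Treatment may affect that, and it may be related to disease course. On-drug values from Weeks 12 and 24 (and Week 36, if months are calendar months) of earlier stoppers are discarded, although they carry information about how those subjects were declining.
- **Off-drug values.** For those who stop after 9 months, the Week 52 value is modelled as observed. That is the treatment-policy handling already used in the FAS run.

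This is the only on-drug efficacy estimate in the visible SAP text, and the trial's stated purpose is to provide data for designing confirmatory studies. A reader who trusts the label would take the PP ratio as the effect of a full year on drug.

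**Working it through.** **Inputs from protocol 12.8.1.** 36 evaluable subjects at 2:1 (24 and 12), CV 70%, one-sided alpha 0.10, target ratio 1.375, 44 randomised, about 18% dropout.

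**The plan's own figures.** SD of log AUC = √ln(1 + 0.7²) = 0.6315. SE of the log ratio = 0.6315 × √(1/12 + 1/24) = 0.223. Power at ratio 1.375 is 55.8% (normal) or 55.1% (t), against 55% stated. At 1.56 it is 76.1% or 75.4%, against 75% stated. 36/(1 − 0.18) gives 44. These reproduce and are not in dispute.

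**How far off drug a PP Week 52 value can be.** Footnote 1 of protocol Table 8-1 says "Study months equal 28 days or 4 weeks". Nine such months are 9 × 28 = 252 days, which leaves 365 − 252 = 113 days to the Week 52 visit. With calendar months (about 274 days) the gap is about 91 days. SAP 4.1.1 ends the on-treatment period 98 days after the last dose. With 28-day months, a subject whose last dose falls between Day 252 and Day 267 (365 − 98) therefore has a Week 52 value at or beyond the end of that window.

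**Effect of selection: closed-form check.** Assumptions, not document figures: liability to stop has correlation 0.5 with poor prognosis on log AUC, and all stops occur before 9 months. Among those retained, mean log AUC shifts by 0.5 × 0.6315 × φ(z)/(1 − p), where p is the proportion stopping and z the corresponding normal quantile.

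- p = 18%: φ(0.915) = 0.262, so the shift is 0.5 × 0.6315 × 0.262/0.82 = 0.101.
- If only active-arm stopping is related to prognosis, the PP ratio at no effect is exp(0.101) = 1.11.
- If only placebo stopping is related, it is exp(−0.101) = 0.90.
- If both arms are related equally, the shifts cancel and the ratio is 1.00.
- With 27% stopping on active and 9% on placebo, related in both arms, the shifts are 0.143 and 0.056, giving exp(0.087) = 1.09.

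If half of the stops come after 9 months, the simulated ratios shrink to 1.05, 0.96, 1.00 and 1.04.

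**Effect of selection: longitudinal simulation.** 400,000 subjects at 2:1, with assumed between-subject slope SD 0.4 per year and residual SD 0.15. The chance of stopping after Weeks 12, 24 and 36 rises with observed decline on active and is constant on placebo.

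| Stopping | True ratio | PP | FAS, post-stop values missing |
|---|---|---|---|
| 14–17% in both arms | 1.00 | 1.03–1.07 | 1.00 |
| 14–17% in both arms | 1.375 | 1.41–1.47 | 1.37–1.38 |
| 21% active, 10% placebo | 1.00 | 1.08 | 1.00 |
| 21% active, 10% placebo | 1.375 | 1.48 | 1.37–1.38 |

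Separate re-runs agreed closely, with an overall PP span of 1.03–1.08 at the null and 1.41–1.49 at 1.375. With dependence on placebo only, PP gave about 0.95 and 1.31. With equal dependence it was unbiased.

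**Consequence at trial size.** With SE 0.223, a spurious ratio of 1.05 raises one-sided rejection from 10% to 14%, and 1.10 raises it to 20%.

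**Effect of the retained off-drug values alone.** Assume 9% per arm stop after month 9, another 9% stop earlier (unrelated to prognosis), and the effect stops accruing at month 9. Late stoppers are then 0.09/0.91 of the PP set and lose a quarter of the log effect: ln 1.375 × (1 − 0.25 × 0.09/0.91) = 0.311, a ratio of 1.364 (simulated 1.363). This is a small dilution; selection is the larger issue.

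**The case against.** The stakes are limited. This is one secondary run in a trial described as non-confirmatory, and the FAS primary and the stated power do not depend on it. That stands. Nothing says the PP ratio will be the planning figure for later studies, and redacted SAP sections may hold other on-drug analyses.

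The bias mechanism is assumed. Subjects and investigators are blinded, and the mandatory stopping reasons do not name falling C-peptide. This stands as a limit on expected size. Blinding does not exclude it, however: several of those reasons (infusion reactions, severe infections, neutropenia) could differ by arm, and SAP 6.1.3.3 itself foresees subjects leaving the study for lack of efficacy or worsening disease.

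The bias can also run downward or be absent, as the working shows. At 1.03 to 1.08 under the null it is 0.03 to 0.08 on the log scale, or about 0.13 to 0.35 of an unadjusted standard error. Both points stand.

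The alternative looks exact because stopping was generated from observed values, which is MAR. That also stands: the simulation does not show robustness when MAR fails.

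The 98-day window and Note 2 of SAP 6.1.3 have been offered in mitigation. The window is applied mainly to safety summaries. Note 2 stops an early end-of-treatment test from counting as Week 52. Neither removes an off-drug value collected on time at Week 52 from the PP model.

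Finally, 18% of 44 is about 8 subjects, but that is the planned dropout rate, not a rate of stopping before month 9. It is only a rough ceiling for the loss from early stopping.

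**Conclusion.** The concern holds. The mismatch between label and analysis can be read from SAP 4.2 and 6.1.3 and needs no simulation: early stoppers are removed entirely, later stoppers contribute off-drug values, and no visible text reconciles either with a hypothetical strategy. Whether the PP ratio is biased depends on stopping being related to disease course differently in the two arms. The simulated shifts of a few per cent up to about 10% in the ratio illustrate what such stopping could do; they are not expected values. They rest on an assumed strength of dependence and on the assumed slope and residual SDs. The weight is moderate: worth correcting before database lock, with no effect on the primary analysis.

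**What to change.** In SAP 6.1.3, define the hypothetical-strategy analysis as follows: FAS, analysed as randomised; C-peptide AUC after permanent treatment discontinuation set to missing; same mixed model under MAR. State the MAR assumption and allow a sensitivity analysis for departures from it. This uses the data rule already in protocol 12.4.3.

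If the PP run is kept, call it a supportive per-protocol analysis without an estimand label, set its post-discontinuation values to missing, and state whether the 9 months are 28-day or calendar months.

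The difference between protocol 12.4.3 and SAP 6.1.3 on post-discontinuation data in the primary analysis is a related but separate matter.

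The cost is SAP wording and one extra model run, with no new data.
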